7.4.1 Analyses of Primary Endpoints

7.4.1.1 Analyses of Primary Immunogenicity Endpoints

For mucosal S-IgA against WCE at Day 29, the two-sided 95% CI for change from baseline in GMFR will be calculated. A superiority hypothesis will be tested to demonstrate BPZE1 can adequately induce mucosal S-IgA against WCE at Day 29 by GMFR.

The formal superiority hypothesis is:

$$H_0: GMFR \leq 1 \text{ vs. } H_A: GMFR > 1$$

The GMFR is defined as the ratio of GMT at Day 29 and GMT at baseline, i.e.,

$$GMFR = \left(\frac{\mu_{D29}}{\mu_{BL}} \right), \text{ with } \mu_{D29} \text{ and } \mu_{BL} \text{ being the GMTs at Day 29 and baseline, respectively.}$$

After natural logarithmic transformation, $\ln(GMFR) = \ln(\mu_{D29}) - \ln(\mu_{BL})$. Therefore, the hypothesis can be expressed in the natural log scale as:

$$H_0: \ln(\mu_{D29}) - \ln(\mu_{BL}) \leq 0 \text{ vs. } H_A: \ln(\mu_{D29}) - \ln(\mu_{BL}) > 0$$

After natural logarithmic transformation, a paired t-test will be used to test the difference of mucosal S-IgA against WCE at Day 29 compared with baseline. The superiority objective will be demonstrated if the lower limit of the 95% CI for the difference of mucosal S-IgA against WCE at Day 29 compared to baseline on the natural log scale is greater than 0 within the treatment group. The superiority hypothesis will be tested in treatment groups BPZE1 and BPZE1 + Boostrix separately.

7.4.1.2 Analyses of Primary Safety Endpoints

The number and percentage of subjects with solicited AEs (local, nasal/respiratory, and systemic reactogenicity events) through 7 days following first study vaccination with any combination of pertussis-containing vaccines (BPZE1, BPZE1 + Boostrix, Boostrix) will be calculated by treatment group.

7.4.2 Analyses of Key Secondary Serum Immunogenicity (IgG) Endpoints

Descriptive statistics (GMT, GMFR, seroconversion) for serum IgG against PT, FHA, and PRN will be presented at baseline and Day 29 and by treatment group (BPZE1 + Boostrix, Boostrix). For serum IgG against PT, FHA, and PRN at Day 29, the two-sided 95% CI for group difference in GMT in natural log will be calculated. A two-sample t-test will be used to compare the natural log-transformed GMTs between groups for serum IgG against each of PT, FHA, and PRN at Day 29. The non-inferiority objective will be demonstrated if the lower limit of the 95% CI of group difference in natural log is greater than -0.693.

For serum IgG against diphtheria and tetanus, the two-sided 95% CI for group difference in the proportion of subjects with antibody concentration ≥ 0.1 international units (IU)/mL will be calculated using the Agresti-Caffo method. The non-inferiority objective will be demonstrated if the lower limit of 95% CI of group difference is greater than -0.1.

The Holm procedure (also known as a stepdown Bonferroni procedure) will be used to control for multiplicity when evaluating the key secondary endpoints.

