7.1 Sample Size Calculations

Approximately 360 subjects will be enrolled and randomly assigned (1:1:1) to 1 of 3 treatment groups (refer to Table 3-1) to contribute to safety and efficacy assessments. Enrolment will be operationally managed at the study level to maintain a minimum number of subjects enrolled in 2 age groups: 6 to 10 years, inclusive; and 11 to 17 years, inclusive. It is estimated that a 10% drop-out rate will occur, allowing for approximately 108 evaluable subjects per treatment group.

Primary immunogenicity endpoints: The sample size is based on calculations to achieve adequate response on Day 29 over baseline of mucosal S-IgA for WCE assay in the BPZE1 and BPZE1 + Boostrix groups. Assuming the GMT follows a log-normal distribution, by applying a natural logarithmic transformation of the GMT, a paired t-test will be used to test the difference of mucosal S-IgA against WCE at Day 29 compared with baseline (equivalent to natural logarithmic transformation of the GMFR). With an effective sample size of N=108 subjects per group, the study provides 95% power for detecting an effect size of 0.35 for each of the two primary comparisons with a two-sided significance level of 0.05. By multiplying the power for each of the two comparisons, the study provides an overall power of 90% (=95%*95%) for testing both primary comparisons. Factoring in an estimated 10% drop-out rate, each treatment group would include approximately 120 subjects for a total of approximately 360 subjects in the study.

Key secondary endpoints: To demonstrate non-interference of IgG serum responses for the Boostrix-containing antigens (diphtheria, tetanus) at Day 29 when BPZE1 is co-administered with Boostrix (BPZE1 + Boostrix vs Boostrix), the test for non-inferiority of BPZE1 + Boostrix to Boostrix for the proportion with titer ≥ 0.1 IU/mL (for diphtheria, tetanus) has power exceeding 92% with approximately N=120 subjects per treatment group, assuming a noninferiority margin of -0.1, one-sided significance level of 0.025, 10% drop-out rate and the proportion with titer ≥ 0.1 IU/mL for the Boostrix treatment being at least 0.95.

To demonstrate non-interference of IgG serum responses for the Boostrix-containing antigens (PT, FHA, PRN) at Day 29 when BPZE1 is co-administered with Boostrix (BPZE1 + Boostrix vs Boostrix), the tests for non-inferiority of BPZE1 + Boostrix to Boostrix for each of the three IgG parameters (PT/FHA/PRN) have power of 97%, 100%, and 88%,

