MAAE	medically attended adverse event
MAD	mucosal atomization device
MedDRA	Medical Dictionary for Regulatory Activities
OTC	over the counter
PBMC	peripheral blood mononuclear cell
PCR	polymerase chain reaction
PRN	pertactin
PT	pertussis toxin
PT	preferred term
RRR	reduction of relative risk
SAE	serious adverse event
SAP	statistical analysis plan
S-IgA	secretory immunoglobulin A
SMC	safety monitoring committee
SOC	system organ class

SUSAR	suspected unexpected serious adverse reaction
Tdap	tetanus toxoid, reduced diphtheria toxoid, and acellular pertussis
WCE	whole cell extract
wP	whole cell pertussis

1. Introduction

This statistical analysis plan (SAP) describes the analyses and data presentations for ILiAD's protocol IB-201P "A Phase 2b, Multi-Center, Placebo-Controlled, Randomized Study of BPZE1 Intranasal Pertussis Vaccine in Healthy School-Age Children to Assess the Immunological Response and Safety Profile of a Single Dose BPZE1 With and Without Co-Administration of Tetanus, Diphtheria, and Acellular Pertussis (Boostrix™)" which was issued on 03FEB2021 (amended 02APR2021, 09JUN2021, 07JUL2021, 16AUG2021, 30MAY2022, and 30MAR2023 (still in use in countries outside Costa Rica), 10OCT2023 (applicable in Costa Rica only)). It contains definitions of analysis populations, derived variables, and statistical methods for the analysis of immunogenicity, colonization (substudy only) and safety.

These analyses include one (1) interim analysis and one final analysis. The purpose of the SAP is to ensure the credibility of the study findings by pre-specifying the statistical approaches to the analysis of study data prior to database lock and any data analysis for the interim/final analyses. This SAP is to be interpreted in conjunction with the protocol. Should the SAP and protocol be inconsistent with respect to the planned analyses, the language of the SAP is governing. This SAP will be finalized and signed prior to the clinical database lock for the interim analyses. If the final clinical study report (CSR) contains changes to any planned statistical analyses, the justification for any such differences will be fully documented in the CSR. All statistical analyses detailed in this SAP will be conducted using SAS® Version 9.4 or higher.

2. Objectives

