2.2. Secondary Objectives

2.2.1. Key Secondary Objective

- To demonstrate non-interference of immunoglobulin G (IgG) serum responses for all Boostrix-containing antigens (diphtheria, tetanus, pertussis toxin [PT], filamentous hemagglutinin [FHA], pertactin [PRN]) at Day 29 when BPZE1 is co-administered with Boostrix (BPZE1 + Boostrix vs Boostrix).

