8.2. Analyses of Key Secondary Serum Immunogenicity (IgG) Endpoints

Descriptive statistics (GMT, GMFR) for serum IgG against PT, FHA, and PRN will be presented at baseline and Day 29 and by treatment group (BPZE1 + Boostrix, Boostrix).

The non-interference objective will be tested as non-inferiority of BPZE1+Boostrix group compared to the Boostrix group.

The formal non-inferiority hypothesis is:

$$H_0: \frac{\mu_{BBP}}{\mu_B} \leq 0.5 \text{ vs. } H_A: \frac{\mu_{BBP}}{\mu_B} > 0.5$$

Taking the natural log transformation,

$$H_0: \ln(\mu_{BBP}) - \ln(\mu_B) \leq -0.693 \text{ vs. } H_A: \ln(\mu_{BBP}) - \ln(\mu_B) > -0.693$$

Where μ_{BBP} is the GMT for the BPZE1+Boostrix group and μ_B is the GMT for the Boostrix group.

For serum IgG against PT, FHA, and PRN at Day 29, separate ANCOVA models that include baseline IgG levels and treatment group as covariates will be used to compare the natural log-transformed GMTs between BPZE1 + Boostrix and Boostrix groups. The 95% CI for between group difference in GMT will be calculated in two steps: 1) calculate the 95% CI on natural log scale; 2) exponentiate the lower and upper limits to get the 95% CI on the original scale.

Non-inferiority, or non-interference, will be demonstrated if the lower limit of the 95% CI of between group difference in natural log-transformed GMTs is greater than -0.693.

For serum IgG against diphtheria and tetanus, the non-interference objective will be tested as non-inferiority of BPZE1+Boostrix group compared to the Boostrix group for the proportion of subjects with antibody concentration ≥ 0.1 IU/mL.

The formal hypotheses is:

$$H_0: \pi_{BBP} - \pi_B \leq -0.1 \text{ vs. } H_A: \pi_{BBP} - \pi_B > -0.1,$$

where π_{BPP} is the proportion of subjects with antibody (diphtheria or tetanus) concentration ≥ 0.1 IU/mL for the BPZE1+Boostrix group and π_B is the corresponding proportion for the Boostrix group.

The 95% CI for between group difference in the proportion of subjects with antibody concentration ≥ 0.1 IU/mL will be calculated using the Agresti-Caffo method. Non-inferiority, or non-interference, will be demonstrated if the lower limit of this 95% CI is greater than -0.1.

Sensitivity analysis for key secondary endpoints will be performed based on the Immunogenicity Analysis Set.

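### The key secondary decision rule is unsettled (Holm in the protocol, unadjusted 95% intervals in the success criteria), and the stated diphtheria/tetanus power is nearly 3 points too high for the planned Agresti-Caffo interval

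*Protocol*

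**What the plan says.** **Multiplicity.** The protocol names Holm for the key secondary endpoints in three places: the Synopsis (Statistical Methods), Section 7.4 and Section 7.4.2. The last reads: "The Holm procedure (also known as a stepdown Bonferroni procedure) will be used to control for multiplicity when evaluating the key secondary endpoints". Section 7.4.2 also gives each antigen's success rule as an ordinary two-sided 95% interval against its margin.

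**SAP rule.** SAP 8.2 sets five success rules and no adjustment. For PT, FHA and PRN, success requires that "the lower limit of the 95% CI of between group difference in natural log-transformed GMTs is greater than -0.693". For diphtheria and tetanus: "Non-inferiority, or non-interference, will be demonstrated if the lower limit of this 95% CI is greater than -0.1", where the interval "will be calculated using the Agresti-Caffo method". Holm is not mentioned anywhere in the SAP.

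**Precedence.** The SAP Introduction says the SAP is to be read together with the protocol, and: "Should the SAP and protocol be inconsistent with respect to the planned analyses, the language of the SAP is governing". SAP Section 11 (Changes in the Planned Analysis) lists only the added 10 to 17 year age group.

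**Scope.** SAP 2.2.1 gives the objective as: "To demonstrate non-interference of immunoglobulin G (IgG) serum responses for all Boostrix-containing antigens". For the primary endpoint, Protocol 7.4 and SAP 8.1 say that both comparisons must succeed. There is no matching sentence for the five antigens.

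**Power.** Protocol 7.1 and SAP 4.1.2 say that the diphtheria/tetanus test "has power exceeding 92% with approximately N=120 subjects per treatment group", at one-sided 0.025, margin 0.1, 10% drop-out and a Boostrix proportion of at least 0.95. SAP Table 4-1 gives 92.1%.

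**The concern.** Holm over five one-sided tests at 0.025 compares the smallest p-value with 0.025/5 = 0.005, which corresponds to a 99% interval, and then relaxes step by step. Five ordinary 95% intervals use 0.025 throughout. These are different rules. Protocol 7.4.2 contains both, and SAP 8.2 contains only the second.

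Which rule is needed depends on the claim. If the objective is met only when all five antigens pass, no adjustment is required. If antigens may be claimed one at a time, it is. The documents do not say which applies. A choice made after Day 29 results are seen by treatment group would be open to the charge of being data-driven.

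The power figure is a separate and smaller matter: it does not belong to the interval that will be used to judge success.

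**Working it through.** **Inputs.** Evaluable subjects 108 per arm (120 less 10%), proportion 0.95 in both arms, margin 0.1, one-sided 0.025 (Protocol 7.1; SAP 4.1.2 and Table 4-1). Interval method: Agresti-Caffo (Protocol 7.4.2, SAP 8.2).

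**1. Can the two rules disagree on the same data?** Suppose PT, FHA and PRN pass easily, and diphtheria and tetanus each show 100/108 (BPZE1 + Boostrix) against 103/108 (Boostrix). Agresti-Caffo adds one success and one failure per arm:

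- Proportions: 101/110 = 0.9182 and 104/110 = 0.9455; difference -0.0273.
- Standard error: sqrt[(0.9182 × 0.0818 + 0.9455 × 0.0545)/110] = 0.0339.
- Lower limit at one-sided 0.025: -0.0273 - 1.960 × 0.0339 = -0.094. Both antigens pass.
- Holm with two hypotheses left uses 0.025/2 = 0.0125: -0.0273 - 2.241 × 0.0339 = -0.103. Both antigens fail.

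**2. Family-wise error for unadjusted single-antigen claims.** With all five null hypotheses true at their boundaries:

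- Independent tests: 1 - 0.975^5 = 11.9%.
- Upper bound: 5 × 0.025 = 12.5%.
- If all five must pass, a false overall claim requires a false pass on at least one truly inferior antigen, so the error is at most the nominal 2.5%. (Agresti-Caffo is itself approximate: its exact size at 0.85 against 0.95 with 108 per arm is 2.8%.)

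**3. Reproducing the stated power.** Unpooled Wald approximation:

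Phi[0.1/sqrt(2 × 0.95 × 0.05/108) - 1.96] = Phi(3.372 - 1.960) = 92.1%.

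This matches SAP Table 4-1. The other entries agree within 0.6 points.

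**4. Power of the planned interval.** Both binomial distributions were enumerated exactly, counting success when the Agresti-Caffo lower limit exceeds -0.1:

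| True proportion, both arms | SAP Table 4-1, N=120 | Agresti-Caffo, 108 evaluable |
|---|---|---|
| 0.92 | 77.3% | 75.5% |
| 0.95 | 92.1% | 89.4% |
| 0.97 | 99.1% | 97.4% |

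At 0.95 the shortfall is 92.1 - 89.4 = 2.7 points. At 108 per arm, 92% is reached only at a proportion of about 0.956 or more. At 0.95 it would take 117 evaluable per arm (117/0.9 = 130 randomized).

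**5. If Holm is kept.** In a simulation of 100,000 trials with five independent endpoints (independence is an assumption) and proportion 0.95, power per diphtheria or tetanus test is about 87%.

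**The case against.** **The SAP is silent on Holm; it does not reject it.** A reader might infer that the governing plan has removed the adjustment. The documents do not support that. The SAP is to be read with the protocol and prevails only where they are inconsistent. Its general two-sided 0.05 statement also appears in Protocol 7.4, in the paragraph before Holm is named. Nor does Section 11 decide the matter: it also omits the move from a two-sample t-test (Protocol 7.4.2) to ANCOVA (SAP 8.2), so it is not a complete list. This argument stands. It shows an ambiguity, but does not resolve it.

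**The objective points to all five antigens.** On that reading the 11.9% to 12.5% does not apply, and a reader should not take it as the error rate of the stated objective. It holds only for single-antigen claims with every null true. This stands too, but the all-five rule has to be inferred because no sentence states it. Holm would also matter little to the joint claim: in the simulation above, all five pass in 68.5% of trials unadjusted and 67.3% with Holm.

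**The power gap is a planning approximation.** The assumption is at least 0.95, Table 4-1 shows sensitivity to the proportion, and Protocol 7.2 allows a blinded recalculation that re-estimates these proportions. No document names the Wald formula; it is inferred because it reproduces the figures. All fair, but above 92% is still not met at the plan's own lower planning value.

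**Joint power.** A reader might conclude that power for all five is about 68% to 88%. That range uses two-sample t-tests for PT, FHA and PRN, whereas SAP 8.2 specifies ANCOVA with baseline IgG. The baseline correlation is not given. Treating the Table 4-2 SDs as unadjusted and assuming correlations of 0.3, 0.5 or 0.7, PRN power rises from 88% to about 91%, 95% or 99%, so the range does not describe the governing analysis.

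**Conclusion.** The point holds as an inconsistency in the decision rule. The protocol calls for Holm, both documents' success criteria use unadjusted 95% intervals, the governing SAP does not mention Holm, and neither document says whether all five antigens must pass. Antigen-level conclusions can differ on the same data. The family-wise error could reach 11.9% to 12.5% only if antigens are claimed singly without adjustment; under an all-five rule it is at or below the nominal 2.5%.

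The power finding is secondary: about 89.4% per antigen for diphtheria and tetanus instead of above 92%, at 108 per arm and 0.95 in both arms. The gap closes at a proportion of about 0.956.

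**What to change.** Before the interim lock and any unblinded Day 29 results, state one rule in SAP 8.2 and align Protocol 7.4.2 (with 7.4 and the Synopsis). Either is acceptable:

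- The key secondary objective is met only if all five lower 95% limits clear their margins, each at one-sided 0.025, with no adjustment.
- Antigens are claimed singly, using Holm-adjusted p-values or matching confidence limits in place of the fixed 95% limits.

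Record the choice in SAP Section 11.

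In Protocol 7.1 and SAP 4.1.2/Table 4-1, restate the diphtheria/tetanus power as about 89% per antigen at 0.95 with Agresti-Caffo at one-sided 0.025, or about 87% under independence if Holm is kept. If joint power is reported, calculate it for the SAP's ANCOVA with an explicit assumed baseline correlation, and do not insert 68% to 88%.

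The cost is wording and a slightly less favourable stated power, with no extra subjects. Under Protocol 11.2.1 a protocol amendment needs ethics committee approval; a letter of clarification does not.

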7.4.3 Analyses of Secondary Endpoints

7.4.3.1 Analyses of Secondary Mucosal Secretory Immunogenicity (S-IgA) Endpoints

Descriptive statistics (GMT, GMFR, seroconversion) for mucosal S-IgA against WCE, PT, FHA, PRN, and any other anti-pertussis mucosal antibodies identified during assay development will be presented at each time point and by treatment group.

Comparisons between two time points (eg, Day 29 and baseline) will be conducted using a paired t-test as outlined in Section 7.4.1.1. Non-interference or non-inferiority comparisons between two treatment groups (eg, BPZE1 + Boostrix being non-inferior to Boostrix by GMT at Day 29) will be conducted using a two-sample t-test as outlined in Section 7.4.2. Non-inferiority comparisons between two proportions will be conducted using the Agresti-Caffo method as outlined in Section 7.4.2.

Analysis of covariance (ANCOVA) model will be used to examine the effects of age or other baseline demographics on differential responses to induction of mucosal S-IgA immunity.

Subgroup analyses by age (6 to 10 years and 11 to 17 years, inclusive), time since last aP vaccination (prior to study entry), or other baseline demographics and by baseline antibody level (by quantile) will be conducted for BPZE1, BPZE1 + Boostrix, and Boostrix treatment groups. In addition to descriptive summaries, a forest plot of the corresponding 95% CIs will be generated for each subgroup.

Mucosal S-IgA seroconversion rate (2-fold increase over baseline value or a 4-fold increase over the lower limit of assay detection [whenever the baseline value falls below the lower limit of assay detection]) with 95% CI will be calculated by treatment group at Day 29. A chi-square test will be used to compare seroconversion rates between treatment groups. Additional combinations of antibody response (WCE, PT, FHA, PRN, and any additional anti-pertussis antibodies) may also be tested.

Plots of the reverse cumulative distribution curves of each anti-pertussis mucosal antibody titre for mucosal S-IgA GMT will be generated for Day 29 by treatment group.

Further details will be provided in the SAP.

7.4.3.2 Analyses of Secondary Serum Immunogenicity (IgA and IgG) Endpoints

All analyses will use the approaches outlined in Section 7.4.1.1 for the primary analyses, in Section 7.4.2 for the key secondary analyses and those outlined in Section 7.4.3.1 for secondary analyses.

7.4.3.3 Analyses of Secondary Safety Endpoints

The number and percentage of subjects will be summarized for each solicited AE by timepoint, severity grade, and treatment group. Additionally, solicited AEs will be analysed by taking the maximum severity through 7 days following any study vaccination to summarize the frequency and percentage of subjects reporting each local [if applicable; after IM injection only], nasal/respiratory, or systemic event. Mean response (for any measurement) and duration through 7 days following any study vaccination will be summarized daily using descriptive statistics. Solicited AEs will be reported separately following study vaccination on Day 85 in the substudy.

Adverse events will be coded by preferred term and system organ class using the latest version of MedDRA.

The following unsolicited AEs will be summarized as number and percentage of subjects reporting at least 1 event in each preferred term and system organ class and cross-tabulated by severity and relationship to study vaccination.

- All AEs through 28 days following first study vaccination and following re-vaccination/attenuated challenge (substudy) by severity and relationship to study vaccination, and by treatment group.
- All MAAEs through 84 days following first study vaccination and re-vaccination/attenuated challenge (substudy) by treatment group by severity and relationship to study vaccination, and by treatment group and time since study vaccination.
- All AESIs and SAEs through Day 169/EOS by treatment group by severity and relationship to study vaccination, and by treatment group and time since study vaccination.

Serious AEs will be summarized by detailed listing showing the event description, preferred term and system organ class, relevant dates (study vaccinations and AEs), severity, relatedness, and outcome for each event. Any SAE considered related to BPZE1 will be classified as a SUSAR.

The number and percentage of subjects with SARS-CoV-2 infections or AESIs associated with COVID-19 infection or SARs-CoV-2 vaccine-related events will be summarized, if the COVID-19 pandemic remains ongoing in the region or if there are mass vaccinations using a COVID-19 vaccine during study conduct.

The number and percentage of subjects with colonization or clearance by real-time PCR or *B. pertussis* culture following study vaccination (subsets of subjects) will be summarized over time using the methods outlined in Section 7.4.2 for proportions.

Secondary safety endpoints following re-vaccination/attenuated challenge for the optional substudy will be analysed in a similar fashion as the secondary safety endpoints for the main study.

